8.5. Assessment of Safety

Timely, accurate, and complete reporting and analysis of safety information for clinical studies are crucial for the protection of subjects. Reporting and analysis of safety data are mandated by regulatory authorities worldwide. Medtronic has established procedures in conformity with worldwide regulatory requirements to ensure appropriate reporting of safety information. This study is conducted in accordance with these procedures and regulations.

Since the safety reporting requirements and classification systems vary for each regulatory agency, requirements from all geographies are taken into account for the collection and reporting of safety information.

8.6. Recording Data

Data will be collected via electronic Case Report Forms (e-CRFs), Reveal LINQ ICM device interrogation files, and Medtronic CareLink transmissions. A web-based application tool, Remote Data Capture (RDC) will be used for data entry of e-CRFs. The investigator is responsible for the preparation (review and signature) of the e-CRF.

18 December 2018 Version 4.0

Page 36 of 66

Medtronic

8.7. Deviation Handling

A study deviation is defined as an event within a study that did not occur according to the Clinical Investigation Plan or the Clinical Trial Agreement.

Prior approval by Medtronic is expected in situations where the investigator anticipates, contemplates, or makes a conscious decision to deviate. Prior approval is not required when a deviation is necessary to protect the safety, rights or well-being of a subject in an emergency or in unforeseen situations beyond the investigator's control (e.g. subject failure to attend scheduled follow-up visits, inadvertent loss of data due to computer malfunction, inability to perform required procedures due to subject illness).

For medically justifiable conditions which preempt a subject's ability to complete a study-required procedure, it may be permitted to report only one deviation which will apply to all visits going forward. This may also apply for other unforeseen situations (e.g. the subject permanently refuses to complete a study required procedure and the data will not contribute to the primary end point analysis). However, prior approval from Medtronic is required for such situations.

All study deviations must be reported on the Study Deviation e-CRF regardless of whether medically justifiable (e.g. crossover), pre-approved by Medtronic, an inadvertent occurrence, or taken to protect the subject in an emergency. The deviation description must be recorded with an explanation for the deviation. In the occurrence of a corrupted device interrogation file, Medtronic may request a deviation to document that a readable interrogation file is unavailable.

In the event the deviation involves a failure to obtain a subject's consent, or is made to protect the life or physical well-being of a subject in an emergency, the deviation must be reported to the Ethics Committee as well as Medtronic within five (5) working days. Reporting of all other study deviations should comply with Ethics Committee policies and/or local laws and must be reported to Medtronic as soon as possible upon the site becoming aware of the deviation. Reporting of deviations must comply with Ethics Committee policies, local laws, and/or regulatory agency requirements. Refer to Investigator Reports, Table 12 for geography-specific deviation reporting requirements and timeframes for reporting to Medtronic and/or regulatory bodies.

Medtronic is responsible for analyzing deviations, assessing their significance, and identifying any additional corrective and/or preventive actions (e.g. amend the Clinical Investigation Plan, conduct additional training, terminate the investigation). Repetitive or serious investigator compliance issues may result in initiation of a corrective action plan with the investigator and site, and in some cases, necessitate suspending enrollment until the problem is resolved or ultimately terminating the investigator's participation in the study. Medtronic will provide site-specific reports to investigators summarizing information on deviations that occurred at the investigational site on a periodic basis.

18 December 2018 Version 4.0 Page 37 of 66

8.8. Subject Withdrawal or Discontinuation

Subjects will be followed until study closure.

9. Risks and Benefits

Medtronic follows rigorous Quality Assurance and Control procedures throughout the life of a product, from the business analysis phase through development, market release, and post-market surveillance.

The Stroke AF study system and components are commercially released and used in accordance with their approved labeling. The safety and clinical performance of these devices has been demonstrated through previous pre-clinical testing and previous clinical studies. There are no incremental risks introduced to the subject as a result of participation in the Stroke AF study. Devices should be handled in accordance to the Clinical Manual.

For subjects with a Reveal LINQ ICM inserted, Risks and Risk Mitigations to the subject identified below are consistent with those outlined in the device manual. There may be other discomforts and risks related to the device system and/or this study that are not foreseen at this time.

9.1. Potential Risks

Possible risks associated with the Reveal LINQ ICM include but are not limited to the following:

- Risks associated with a minor surgical procedure
- Slight risk of infection
- Sensitivity to the device

9.2. Potential Benefits

The Reveal LINQ ICM may offer no benefit. The potential benefits of having the Reveal LINQ ICM include more intensive follow-up treatment and frequent device transmissions and/or continuous monitoring enabling more precise detection of AF. This better precision to detect AF may lead to clinicians having better data to quantify AF burden. The information gained from this study could result in the improved detection and management of atrial fibrillation. Additionally, information collected from this study may assist in the design of new product(s)/therapy(ies) and/or instructions for use. The System may not offer a direct clinical benefit to study subjects. The information collected from this study may assist in the design of new product(s)/therapy(ies) and/or instructions for use.

9.3. Risk-Benefit Rationale

The potential risks associated with the Reveal LINQ ICM were identified and have been successfully mitigated. Any potential risks associated with this study are further minimized by selecting qualified investigators and training study personnel on the Clinical Investigation Plan.

18 December 2018 Version 4.0 Page 38 of 66

In addition, investigators will be actively involved in the insertion and follow-up of the subjects implanted with the Reveal LINQ system.

Risks will be minimized by careful assessment of each subject prior to, during, and after insertion of the Reveal LINQ ICM. Prior to insertion, it is recommended subjects undergo a complete cardiac evaluation.

After insertion, subjects in the Stroke AF clinical study will be followed at regular intervals. At each protocol required follow-up, the investigator must interrogate the Reveal LINQ ICM and assess for any adverse events.

- Risks associated with a minor surgical procedure
- Slight risk of infection
- Sensitivity to the device

10. Adverse Events and Device Deficiencies

All reported Adverse Events (AEs) must be followed until resolved, ongoing without further actions to be taken, the subject exits the study or until study closure, whichever occurs first. In the event that a subject is exited from the study prior to study closure, all efforts should be made to continue following the subject until all ongoing AEs are resolved or they are ongoing without further actions to be taken.

10.1. Adverse Event Assessment

10.1.1. Adverse Events

All Reveal LINQ ICM system/component-related, Reveal LINQ ICM procedure related, cardiovascular related AEs, and all serious adverse events leading to death will be collected throughout the study duration, starting at the time of signing the consent form.

Reporting of these events to Medtronic will occur on an Adverse Event (AE) e-CRF, including a description of AE, date of onset of AE, date of awareness of site, treatment, resolution, assessment of both the seriousness and the relatedness to the investigational device. Each AE must be recorded on a separate AE Form. Subject deaths are also required to be reported. Refer to Section 10.5 for Subject Death collection and reporting requirements.

Documented pre-existing conditions are not considered AEs unless the nature or severity of the condition has worsened. Additionally, detected arrhythmias (including AF) for which no action is taken are not reportable AEs. Unavoidable Adverse Events, listed in Table 9 need not be reported unless the adverse event worsens or is present outside the stated timeframe post-insertion.

For AEs that require immediate reporting (see Table 11), initial reporting may be done by phone, fax, or on the e-CRF completing as much information as possible, with missing or follow-up information provided as soon as it becomes available. The AE e-CRF must be completed as soon as possible.

18 December 2018 Version 4.0

Page 39 of 66

Medtronic

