3.1. Background

Stroke is a devastating disease. In the United States (U.S.) more than 780,000 people experience a new or recurrent stroke each year; approximately 600,000 of these are first attacks and 180,000 are recurrent attacks. About 20% of patients die within the first year after having a stroke and another 20% are bound to a nursing home for the rest of their life. Furthermore, stroke is the fifth leading cause of death in the U.S. (when considered separately from other cardiovascular diseases) and the leading cause of serious long-term disability in the U.S. (Dariush Mozaffarian, 2015).

Of all strokes, 87% are ischemic (Dariush Mozaffarian, 2015), which occur as a result of decreased or insufficient blood flow to the brain. Patients with ischemic stroke (IS) are often treated with antithrombotic therapy. For most patients with IS, the mainstay of treatment is anti-platelet (AP) therapy with aspirin, clopidogrel, or aspirin+extended release dipyridamole. However, patients with IS who have been diagnosed with atrial fibrillation (AF) are normally treated with long-term oral anticoagulation (OAC), per recommendations within the AHA/ASA 2014 guidelines. OAC is dramatically more effective at preventing recurrent IS than AP therapy in patients with AF (Owen, 2009). In contrast, for patients without AF (or other rare cardiac sources of embolism), OAC has not been shown more effective than AP therapy. Therefore, detection of AF after IS is crucial, as it results in an important change in the administration of antithrombotic therapy from AP to OAC, thereby reducing the risk of recurrent stroke.

Episodes of AF are often asymptomatic, which makes detection of AF based on patient's symptoms unreliable (L. M. Christensen, 2014) (S. Adam Strickberger, 2005). Additionally, due to its episodic nature, AF is difficult to detect via intermittent monitoring techniques (Paul D. Ziegler, 2009). While AHA/ASA guidelines recommend cardiac monitoring of patients for up to 30 days after stroke, the optimum duration of monitoring is not known. It has generally been shown that longer durations of cardiac monitoring result in higher rates of AF detection after stroke. The advent of insertable cardiac monitors (ICM) allows continuous monitoring to detect infrequent episodes of AF for up to 3 years. Longer monitoring periods may be necessary to detect infrequent but clinically important paroxysms of AF (William C. Choe, 2015).

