3.2. Purpose

Medtronic is sponsoring the Stroke AF study. This is a prospective, multi-site, randomized, controlled, non-blinded, post-market study.

The purpose of the Stroke AF study is to compare the incidence rate of AF through 12 months between continuous cardiac rhythm monitoring and standard of care in subjects with a recent IS of presumed known origin (the cause of the stroke is not unknown), specifically due to small vessel disease, large vessel cervical or intracranial atherosclerosis. Upon enrollment subjects will be randomized 1:1 to continuous monitoring arm vs control arm. Subjects randomized to the continuous monitoring arm will have a Reveal LINQ™ ICM inserted within 10 days of the index event and undergo continuous monitoring. Subjects randomized to the control arm will be followed per site specific standard of care. Detection of AF after IS is crucial, as it results in an important change in antithrombotic therapy from AP to OAC, thereby reducing the risk of recurrent stroke in these patients.

This study supports introducing Reveal LINQ ICM into the care pathway in subjects with an ischemic stroke of presumed known origin.

4. Objectives and Endpoints

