10.2. Definitions/Classifications

10.2.1. Adverse Event and Device Deficiency Definitions

Where the definition indicates "device", it refers to any device used in the study.

18 December 2018 Version 4.0

Page 40 of 66

Medtronic

Table 6: Adverse Event Definitions

18 December 2018 Version 4.0 Page 41 of 66

п	
п	Medtronic
п	Meationic

General			
Adverse Event (AE) (Adapted from ISO 14155:2011, 3.2)	Any untoward medical occurrence, unintended disease or injury, or untoward clinical signs (including abnormal laboratory findings) in subjects, users or other persons, whether or not related to the investigational medical device		
	NOTE 1: This definition includes events related to the investigational medical device or the comparator.		
	NOTE 2: This definition includes events related to the procedures involved.		
Adverse Device Effect (ADE)	Adverse event related to the use of an investigational medical device		
(ISO 14155:2011, 3.1)	NOTE 1: This definition includes adverse events resulting from insufficient or inadequate instructions for use, deployment, implantation, installation, or operation, or any malfunction of the investigational medical device.		
	NOTE 2: This definition includes any event resulting from an error use or from intentional misuse of the investigational medical device.		
Device Deficiency (DD) (ISO 14155:2011, 3.15)	Inadequacy of a medical device with respect to its identity, quality, durability, reliability, safety or performance.		
	NOTE: Device deficiencies include malfunctions, use errors and inadequate labeling		
	Relatedness		
Reveal LINQ ICM Procedure Related	An adverse event that occurs that is directly related to the implantation or modification of the Reveal LINQ system.		
Reveal LINQ ICM System Related	An adverse event that results from the presence or performance (intended or otherwise) of any component of the system (including: Reveal LINQ ICM, Programmer, Patient Assistant, and MyCareLink Patient Monitor).		
Cardiovascular Related	An adverse event relating to the heart and the blood vessels or the circulation.		
Seriousness			

18 December 2018 Version 4.0 Page 42 of 66

Medtronic

Complication	An adverse event that results in death, involves any termination of significant device function, or requires invasive intervention.

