### **Exclusion criteria**

- Subject has had a cryptogenic stroke
- Subject has had a cardioembolic stroke
- Subject has untreated hyperthyroidism
- Subject has had a recent myocardial infarction <1 month of stroke
- Subject has had a recent cardiac surgery (e.g. coronary artery bypass surgery (CABG)) <1 month of stroke
- Subject has a mechanical heart valve
- Subject has valvular disease requiring immediate surgical intervention
- Subject has documented prior history of atrial fibrillation or atrial flutter
- Subject has permanent indication for oral anticoagulation
- Subject has permanent contraindication to oral anticoagulation such that detection of AF would not change medical management, based on enrolling investigators judgment
- Subject is enrolled in a concurrent study that may confound the results of this study. Co-enrollment in any concurrent clinical study (including registries) requires approval of the study manager or designee.
- Subject's life expectancy is less than 1 year
- Subject is pregnant
- Subject has or is indicated for implant with a pacemaker, ICD, CRT, or an implantable hemodynamic monitor
- Subject with a medical condition that precludes the patient from participation in the opinion of the investigator

This document is electronically controlled. Printed copies are considered uncontrolled.

Version 2.0 15/MAY/2017

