### ii. Endpoint Definition

AF will be defined as an AF event lasting more than 30 seconds. The first AF episode detected and adjudicated by the endpoint adjudication committee will be used for this analysis.

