### 7.10. Safety Evaluation

Relatedness of adverse events using the CEC adjudication will be summarized using counts and percentages. Seriousness of adverse events using the Medtronic classification will be summarized using counts and percentages. Details of individual adverse events will be listed.

This document is electronically controlled. Printed copies are considered uncontrolled.

Version 2.0 15/MAY/2017

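### AF that is acted on enters the cardiovascular adverse event summary unseparated, so that descriptive count will run higher in the monitoring arm through detection alone

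*Protocol*

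**What the plan says.** Protocol 10.1.1 sets the collection rule for both arms. Besides system- and procedure-related events, "cardiovascular related AEs, and all serious adverse events leading to death will be collected throughout the study duration". Protocol Table 6 (section 10.2.1) defines cardiovascular related broadly: "An adverse event relating to the heart and the blood vessels or the circulation". Section 10.1.1 then gives the only exemption that concerns AF: "detected arrhythmias (including AF) for which no action is taken are not reportable AEs".

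The protocol expects action to follow detection. Section 3.2 states: "Detection of AF after IS is crucial, as it results in an important change in antithrombotic therapy from AP to OAC". The eligibility criteria, in both documents, exclude anyone for whom this would not apply: "Subject has permanent contraindication to oral anticoagulation such that detection of AF would not change medical management".

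For the safety tables, SAP 7.10 says: "Relatedness of adverse events using the CEC adjudication will be summarized using counts and percentages". Seriousness is summarized in the same way, and individual events are listed. SAP Table 2 assigns the adverse event summary to the ITT cohort, which SAP 7.1.3 defines by randomized arm. Protocol Table 7 makes cardiovascular related one of the three relatedness classes, beside system related and procedure related. Neither document separates AF from other cardiovascular events in the adverse event summary.

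AF is also the efficacy endpoint: "The first AF episode detected and adjudicated by the endpoint adjudication committee will be used for this analysis".

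**The concern.** The randomized difference between the arms is how intensively AF is sought, and the trial is powered on the resulting difference in detection. If a detection that leads to a change of therapy is also recorded as a cardiovascular adverse event, the same finding is counted twice: as an endpoint in the efficacy analysis and as an untoward event in the safety summary. A count by arm would then show more cardiovascular events in the monitoring arm even if the two groups had identical disease and identical outcomes. A reader of the aggregate line could not tell how much of a gap, if any, is something other than detection.

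**Working it through.** **Does acted-on AF enter the adverse event data?** No sentence says so outright. The inference has three steps: all cardiovascular related events are collected; AF relates to the heart; and the exemption for AF applies only where no action is taken. An exemption limited in that way has little purpose unless AF with action is reportable. The documents do not define action, and they do not give the share of detections expected to lead to it.

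**Inputs.** From Protocol 12.1 and SAP 6.1: 486 randomized 1:1, so 243 per arm; one-year event-free rates of 92% (monitoring) and 98% (control); annual attrition 10%; annual crossover 5%. From Protocol 12.2 and SAP 6.2: event-free rates of 80% and 97% for the secondary objective, given without a time point.

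**Reproducing the plan's figures.**
- ln(0.92)/ln(0.98) = 4.13, as stated.
- ln(0.80)/ln(0.97) = 7.33, as stated.

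For expected first-AF subjects, let h be the hazard in the assigned arm, k the hazard in the other arm, x = −ln(0.95) = 0.0513 for crossover and l = −ln(0.90) = 0.1054 for loss. With A = h + x + l, B = k + l and I(r) = (1 − e^(−rT))/r:

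expected subjects = 243 × [h·I(A) + k·x·(I(B) − I(A))/(A − B)]

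The first term counts events before crossover and the second counts events after it. At T = 1 year, with hazards of 0.0834 and 0.0202:
- monitoring: 18.0 + 0.1 = 18.1
- control: 4.5 + 0.5 = 5.0

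The total is 23.1, which matches the plan's 23 events.

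**Excess in the adverse event count.** Let s be the share of detections acted on, assumed equal in both arms, with one AF event per subject. The range of 0.5 to 1.0 for s is an assumption.

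| Horizon and reading | Monitoring | Control | Excess, s = 1 | Excess, s = 0.5 |
|---|---|---|---|---|
| 12 months | 18.1 | 5.0 | 13.2 | 6.6 |
| 3 years, 80%/97% read as 3-year rates | 39.5 | 8.8 | 30.7 | 15.4 |
| 3 years, 80%/97% read as 5-year rates | 24.7 | 5.4 | 19.3 | 9.7 |

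Excesses are computed before rounding. At 12 months they are 6.6/243 = 2.7 to 13.2/243 = 5.4 percentage points.

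**Direction.** The excess lies in the monitoring arm for any equal share above zero. If the shares differ, it reverses only when the control share exceeds 18.1/5.0 = 3.6 times the monitoring share. With every control detection acted on, fewer than 5.0/18.1, or about 27%, of monitoring-arm detections would have to be acted on.

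**Effect on a pooled line.** Suppose both arms have the same 10% risk of any other cardiovascular event, independent of AF, with all AF acted on and no attrition or crossover (assumptions for illustration). At 12 months the pooled proportions are:
- monitoring: 1 − 0.90 × 0.92 = 17.2%
- control: 1 − 0.90 × 0.98 = 11.8%

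The whole gap of 5.4 points comes from detection.

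**The case against.** The case for leaving the plan alone has several sound parts.

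- **No test depends on this.** Neither document has a safety objective or a between-arm test of adverse events. SAP 7.10 gives counts and percentages and does not name arm columns, whereas SAP 7.6 does. The by-arm reading rests on the ITT definition. This stands: the risk is a misleading descriptive imbalance.
- **Device harm is read elsewhere.** A reader might infer that AF detections will appear as harm caused by the device. The documents do not support that. Only system- or procedure-related events are classed as complications or observations, and a detected AF would ordinarily be cardiovascular related only.
- **Recurrent stroke is not hidden.** A reader might also infer that the AF excess could mask a difference in recurrent stroke. It does not follow. Stroke and TIA recurrence has its own data collection (Protocol 8.4.5) and committee adjudication (Protocol 11.1), and SAP 7.8 reports adjudicated stroke within each arm. Deaths are adjudicated separately too.
- **AF can be separated afterwards.** Each event gets a MedDRA term, individual events are listed, and SAP 7.8 reports adjudicated AF events by arm. This is true, but a split chosen after the data are seen, in an unblinded trial analysed by the sponsor, is weaker than one written down beforehand.
- **The reporting step is an inference, and the size rests on assumptions.** Both are correct, and both limit the conclusion. Investigators may not all regard a sought diagnosis as an untoward event.

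The documents also refer to ancillary objectives that are not visible in the available text, so whether cardiovascular events are analysed further there cannot be judged.

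**Conclusion.** The point holds as a descriptive one. On the plain reading of the collection rule, acted-on AF becomes a cardiovascular related adverse event, and the planned summary does not separate it. The resulting count is expected to favour the control arm by about 6.6 to 13 subjects at 12 months. At 3 years the gap is about 15 to 31 if 80% and 97% are 3-year rates, and about 10 to 19 if they are 5-year rates.

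These figures assume the plan's AF rates, attrition and crossover, an equal acted-on share of 50% to 100% in both arms, and one AF event per subject. The direction is more secure than the size. Primary and secondary inference, the device- and procedure-related summaries, and the separate reporting of stroke and death are untouched. This is a low-cost improvement to the safety presentation, not an error that threatens the trial's conclusions.

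**What to change.** In SAP 7.10, present cardiovascular related adverse events and serious adverse events by randomized arm, with and without AF, split by the coded MedDRA term:

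- row (a): AF;
- row (b): all other cardiovascular related events.

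Add a note that row (a) overlaps the efficacy endpoint and reflects unequal detection between the arms. Overlap is the right word: row (a) would hold only AF reported as an adverse event, which need not be the same set as adjudicated first AF. The split remains descriptive and does not turn row (b) into a formal safety comparison.

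The cost is a sentence or two of SAP wording and one extra table row. No new data are needed. No AF event is removed: AF with clinical consequences such as hospitalization stays visible in row (a) and in the serious event count.
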